## 6.0 Multi-Site Research: Not Applicable

## **7.0** Study Timelines

#### 7.1 Timelines

We anticipate that we will need approximately 2 years to enroll the sample size for this study. Participants will remain on the study for up to 1 year.

## 8.0 Study Endpoints

- 8.1 Primary endpoint: The primary endpoint of this pilot RCT is to assess the feasibility of the intervention. The proposed intervention app will be deemed feasible if at least 60% (95% CI +/- 12%) of eligible patients are enrolled in the study, and of those enrolled, at least 60% engage with at least 70% of the intervention modules. Modules engagement will be captured by the app.
- 8.2 Secondary endpoints:
  - Compare patient-reported global satisfaction with sex (PROMIS Sexual Function and Satisfaction Measure) scores at 8 weeks between the study groups
  - Compare patient-reported interest in sexual activity (PROMIS Sexual Function and Satisfaction Measure Interest in sexual activity domain) scores at 8 weeks between the study groups
  - Compare patient-reported global satisfaction with sex (PROMIS Sexual Function and Satisfaction Measure Global satisfaction with sex domain) at 12 weeks between the study groups
  - Compare patient-reported interest in sexual activity (PROMIS Sexual Function and Satisfaction Measure Interest in sexual activity domain) at 12 weeks between the study groups
  - Compare patient-reported orgasm (PROMIS Sexual Function and Satisfaction Measure Orgasm domain) at 8 weeks and 12 weeks between the study groups
  - For males: compare patient-reported erectile function (PROMIS Sexual Function and Satisfaction Measure Erectile function domain) at 8 and 12 weeks between the study groups

- For females: compare patient-reported lubrication and vaginal comfort (PROMIS Sexual Function and Satisfaction Measure lubrication and vaginal comfort domains) at 8 and 12 weeks between the study groups
- Compare patient reported QOL (FACT-BMT) at 8 and 12 weeks between the study groups
- Compare patient reported anxiety and depression symptoms (HADS) at 8 and 12 weeks between the study groups

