#### 3.0 Inclusion and Exclusion Criteria

We will recruit a total of 60 HCT survivors who are at least 3 months post-HCT and without evidence of disease from Massachusetts General Hospital Cancer Center and Dana-Farber Cancer Institute to participate in this randomized trial.

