#### 9.0 Procedures Involved

#### 9.1 Study Design

We will conduct a single-site pilot randomized trial in 60 HCT survivors to assess the feasibility and preliminary efficacy of the intervention for improving patient-reported sexual function, QOL, and mood. Patients will be randomized in 1:1 fashion and stratified by transplant type (autologous vs. allogeneic) to either receive only a sexual health visit with a transplant clinician specializing in sexual health or a sexual health visit with a transplant clinician specializing in sexual health with access to the app. This visit may be in clinic or conducted via secure video-based conference. As transplant type is an important variable that affects sexual function and recovery post-HCT, we will stratify by HCT type to ensure balanced representation between the study groups. Both study groups will attend a visit with a transplant clinician specializing in sexual health who will conduct a brief examination and assess the need for any treatments or medications to address sexual health problems; this visit may be in clinic or conducted virtually via secure video-based conference.. The intervention group will have access to the mobile app. We will also conduct qualitative interviews with 10 patients that are randomized to the mobile app intervention, in order to understand and assess patient experience using the app. Qualitative interviews will be conducted in clinic, or over the telephone.

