#### 9.2 Procedures

We will recruit 60 patients 3 months after autologous or allogeneic HCT who report having sexual dysfunction causing distress for this study. The research assistant (RA) will review the consent form with potential participants and obtain verbal or written informed consent. Upon study enrollment, participants will complete baseline study measures and then they will be randomized to the mobile app versus enhanced standard care.

**Intervention Arm:** Patients randomized to the intervention will first meet with a transplant clinician, in clinic or via secure video-based conference, for a brief medical examination to assess the need for medications for erectile dysfunction, vaginal atrophy, or vulvovaginal GVHD given their prevalence in this population. We will then provide patients with a tablet computer that they will use to access the mobile app. We chose to use tablet computers for intervention delivery in this proof-of-concept study. However, the mobile app can be further adapted in the future to be delivered via mobile phones to enhance dissemination. Upon study enrollment, the RA will provide patients with a comprehensive tutorial and detailed instructions regarding how to use the app, in person or via secure video-based conference. The RA will encourage patients to engage their partners with the app content. The app will also prompt patients to engage their partners with specific exercises. Given the pilot nature of this study, we will not measure the effect of the intervention on partners. Patients will complete the intervention modules at their desired pace over 8 weeks. The app will prompt patients with reminders to complete their modules and utilize incentives to enhance patient engagement, as noted previously. The mobile app

will collect data on intervention fidelity (the number of completed modules, proportion of each module completed, time spent on each module, partner engagement with each module). Participants will complete additional surveys 8 and 12 weeks after clinician consult and examination.

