## 10.0 Data and Specimen Banking: Not Applicable

## 11.0 Data Management and Confidentiality

11.1 Analysis **Data analysis Aim 1 (feasibility):** We will report baseline characteristics of all study participants. The primary endpoint of the proposed study is feasibility. The proposed intervention app will be deemed feasible if at least 60% (95% CI +/- 12%) of eligible patients are enrolled in the study, and of those enrolled, at least 60% engage with at least 70% of the intervention modules (modules engagement will be captured by the app). The 60% feasibility and intervention module completion cut-off is commonly used in behavioral intervention studies. We will also use descriptive statistics to examine the usability of the mobile app based on the system usability scale.

Data analysis Aim 2 (preliminary efficacy): We will compare patients' sexual function (PROMISE Sexual Function and Satisfaction), QOL (FACT-BMT), and depression (HADS) at week-8 and week-12 using analysis of covariance adjusting for baseline values. Mixed linear models will be fitted to adjust for selected demographic and clinical factors when examining change in outcomes of interest across all time points. We will also test for potential moderators of the intervention effect using interaction terms for the mixed linear models to assess whether differences in patient-reported outcomes are moderated by patient factors (age, gender, computer experience), or transplant type. We will use conservative (alpha=0.05) and liberal (alpha=0.25) values to assess statistical significance in this pilot study. When handling missing data, if data appear to be missing at random, we will employ multiple imputation. If data are not missing at random, we will employ pattern mixture modeling.

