#### 11.2 Power Analysis

The primary aim of the proposed pilot is feasibility. We chose the sample size of 60 patients based on the feasibility of completing the project during the proposed timeframe and the ability to assess the preliminary efficacy of the intervention. In a pilot study, at least 30 patients are needed in each group to estimate a parameter.  Thus, the proposed sample size will provide us with preliminary data that can be used to determine the effect size and adequately power future trials. Based on our prior pilot study, with a sample size of 60, we would have >80% power to detect a clinically significant 7-point difference in satisfaction with sex (SD=8) between the two groups.

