## 23.0 Local Number of Subjects:

We anticipate that 60 subjects will be recruited from MGH, BIDMC and DFCI. Based on our prior data, approximately one third of HCT recipients will screen positive for sexual dysfunction causing distress. Therefore, we anticipate that we will screen approximately 200 patients to identify 60 subjects eligible for study participation. 10 patients randomized to the intervention will undergo qualitative interview to assess perceptions and experience of using the mobile application.

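### The ±12% beside the 60% enrollment criterion (8.1, 11.1) does not fit 60 enrolled patients; at the threshold the half-width is about ±10 points

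*Combined protocol and SAP*

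**What the plan says.** Section 8.1 makes feasibility the primary endpoint, in two parts. The first requires "at least 60% (95% CI +/- 12%) of eligible patients are enrolled in the study". The second requires that at least 60% of those enrolled engage with at least 70% of the modules. Section 11.1 repeats the rule: "The proposed intervention app will be deemed feasible if at least 60% (95% CI +/- 12%) of eligible patients are enrolled". Neither section gives a denominator, an interval method or a derivation for the ±12%.

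Sixty is the number enrolled throughout:
- Section 3.0: "We will recruit a total of 60 HCT survivors".
- Section 9.1: a "pilot randomized trial in 60 HCT survivors".
- Section 9.2: "We will recruit 60 patients 3 months after autologous or allogeneic HCT".
- Section 11.2: "We chose the sample size of 60 patients based on the feasibility of completing the project during the proposed timeframe". This section has no precision calculation for either feasibility proportion.

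Section 23.0 expects 60 subjects to be recruited from the three hospitals. It then says that "approximately one third of HCT recipients will screen positive for sexual dysfunction causing distress" and that "we anticipate that we will screen approximately 200 patients to identify 60 subjects eligible for study participation". Section 2.2 reports that in the earlier pilot 50 of 151 (33.1%) screened positive and 47 of those 50 (94.0%) agreed to take part.

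**The concern.** The ±12% looks like an interval computed on about 60 patients, but for this proportion 60 is the planned numerator. The denominator is everyone eligible, including those who decline, and it exceeds 60 unless nobody declines.

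This is the only precision statement attached to the primary endpoint, and it is printed twice. A reader would take the enrollment rate to be less precise at the threshold than it will be, and could not trace the figure to a denominator. Section 23.0 adds to the confusion by using 60 for both the eligible and the recruited count. The endpoint cannot be computed unless eligible patients are counted separately from enrolled ones.

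**Working it through.** **Inputs.** Threshold 0.60 and half-width 12 points (8.1, 11.1); 60 enrolled (3.0, 9.1, 9.2, 11.2, 23.0); about 200 screened and one third positive (23.0); 50/151 positive and 94% uptake in the pilot (2.2); 1:1 randomization (9.1).

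**1. Reproduce the printed figure.** The Wald half-width is h = 1.96 × √(p(1−p)/n), with p = 0.60.
- n = 60: 1.96 × √(0.24/60) = 12.4 points
- n = 64: 12.0
- n = 67: 11.7
- n = 69: 11.6

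The value rounds to 12 only for n = 60 to 69. By other methods the range is 56 to 66 (Wilson, Agresti-Coull), 57 to 67 (Jeffreys), 65 to 75 (Clopper-Pearson) and 67 to 78 (continuity-corrected Wald).

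**2. Use the denominator that the plan implies.** With 60 enrolled at the threshold, eligible = 60/0.60 = 100, and h = 1.96 × √(0.24/100) = 9.6 points (50.4% to 69.6%). Other methods at 60 of 100: Wilson 9.4, Agresti-Coull 9.4, Jeffreys 9.5, Clopper-Pearson 10.0, continuity-corrected Wald 10.1.

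**3. Try every other uptake rate.** With 60 enrolled and uptake u, n = 60/u, so h = 1.96 × u × √((1−u)/60). The maximum is at u = 2/3: 1.96 × 0.667 × √(0.333/60) = 9.7 points. Varying the eligible number from 60 to 400, the maximum is 9.6 for Wilson, Agresti-Coull and Jeffreys, 10.2 for Clopper-Pearson and 10.3 for continuity-corrected Wald. None reaches 12. At the pilot's 94% uptake, h is 5.8.

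**4. Work back from ±12.** With 60 to 69 eligible, 60% uptake gives 0.60 × 60 = 36 to 0.60 × 69 = 41 enrolled (34 to 47 using the ranges of all six methods), not 60.

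**5. Compare with section 23.0.** 200 × 1/3 = 66.7 eligible (200 × 50/151 = 66.2). A denominator of 60 or 67 reproduces ±12 (12.4 or 11.7). But 67 × 0.60 = 40 enrolled, so this forecast, 60 enrolled and 60% uptake cannot all hold.

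**6. The second criterion.** Only the app arm can engage with modules, so it rests on about 60/2 = 30 patients: 1.96 × √(0.24/30) = 17.5 points at 60% (16.5 to 19.2 across the same methods).

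**The case against.** The strongest reply is that ±12 has a visible source. Section 23.0 prints an eligible count of 60, or about 67 at its own one-third rate, and either gives ±12. The number enrolled gives it as well. A reader might therefore infer either that the figure is sound or, going the other way, that it cannot be obtained from the plan at all. The documents support neither reading. The figure can be traced to a number in the plan, but that number of eligible patients at 60% uptake yields only 36 to 40 enrolled. Which number the authors used is not stated.

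A second reply is that little depends on it. This stands. The rule reads as a point estimate of at least 60%, section 11.2 does not base the sample size on this interval, and the observed interval can be computed from the actual eligible count.

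A third is that a tighter figure could flatter the joint endpoint, because engagement is estimated on half the patients. This also stands, and the new wording should allow for it.

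A reader might further infer that screening 200 is too few. The documents do not support that. At the pilot's 94% uptake, 66.7 eligible gives 62.7 enrolled. At 60% uptake it would give 40, but 60% is the floor for declaring feasibility, not a forecast, and nothing caps screening at 200.

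**Conclusion.** The printed ±12% is inconsistent with enrolling 60 patients. At the 60% threshold the half-width is about ±10 points, so the plan overstates it by about 2 points. The finding does not depend on the interval method, since all six give 9.4 to 10.1 at 60 of 100. It rests on 60 being enrolled as planned and on the denominator being all eligible patients, as the criterion is worded. The ±10 applies at the threshold only; at higher uptake, such as the pilot's 94%, the interval is narrower.

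The error is conservative. It changes no feasibility decision and gives no reason to alter the sample size or to doubt accrual. It merits correction because it stands beside the primary endpoint and correcting it is nearly free. In section 23.0 the defect is one of wording: 60 cannot be both the eligible and the recruited count unless every eligible patient enrolls.

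**What to change.** In 8.1 and 11.1, replace the ±12% with: *95% CI about ±10 points at the 60% threshold (60 enrolled of about 100 eligible)*. State that this applies to the enrollment criterion only, because the engagement criterion rests on about 30 app-arm patients (about ±17.5 points at 60%, Wald).

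In 23.0, separate eligible from recruited: about 200 screened at one third positive gives about 67 eligible, from whom 60 are to be recruited.

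The cost is wording in three sections, with no added participants or procedures. The one drawback is that the wide interval for engagement becomes visible.

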#### 1.2 Hypotheses

Hypothesis 1: The intervention will be will be deemed feasible if at least 60% of eligible patients enroll in the study, and of those enrolled, at least 60% engage in at least 70% of the intervention modules.

Hypothesis 2: Patients randomized to the intervention will report better sexual function, QOL, and depression and anxiety symptoms compared to those randomized to the control arm.

Exploratory Aim: to qualitatively explore patients' general perceptions of the sexual health mobile app and their overall satisfaction with the intervention.

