Additionally, we will conduct qualitative interviews with 10 patients who are randomized to the intervention arm, to understand their experience of using the application and to assess patient opinions regarding the app. We will purposefully sample patients to ensure adequate representation based on age and sex. If we see different themes emerge based on age/sex, we will amend the protocol to increase our sample size for these qualitative interviews. We have developed a semi-structured qualitative interview guide to explore 1) patients' general experience using the SHIFT app and 2) patients' opinions regarding app content (Appendix M). Qualitative interviews will be conducted after patients complete all of their quantitative study assessments. Trained study staff will conduct and audio-record one-on-one interviews with patients via telephone or in-person. The estimated time to complete the patient qualitative interview is approximately 30 minutes. Audio recordings of the qualitative interviews will be stored for six months following interview completion.

Enhanced Standard Care: Patients assigned to the enhanced standard care group will not receive the mobile app. However, they will meet with a transplant clinician for a brief medical examination to assess the need for medications for erectile dysfunction, vaginal atrophy, or vulvovaginal GVHD; this visit will be conducted in clinic or virtually via secure video-based conference. The treating transplant clinician may refer patients to a psychologist, urologist, or gynecologist at the patients' request or at their discretion. At MGH, < 1% of transplant survivors are referred to a specialist to address sexual health concerns. Importantly, we did not see an increase in rate of referral to specialists during our pilot study. We will also collect data on referrals to specialists in both study groups. Although most transplant practices across the country do not systematically screen or treat sexual dysfunction, we chose a conservative control group to allow us to most accurately assess the effect of the mobile app.61 Participants will complete additional surveys 8 and 12 weeks after clinician consult and examination.

Institutions will register eligible participants in the Clinical Trials Management System (CTMS) OnCore as required by DF/HCC SOP REGIST-101.

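### The engagement half of the primary endpoint is a share of everyone enrolled, but only the app arm can engage, so the 60% bar cannot be reached as written

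*Combined protocol and SAP*

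**What the plan says.** The feasibility rule has two halves: a share of eligible patients who enrol, and a share who use the app enough. The second half appears three times, each time with enrolled patients as the denominator:

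- Section 8.1 (primary endpoint): "of those enrolled, at least 60% engage with at least 70% of the intervention modules".
- Section 1.2 (Hypothesis 1): "of those enrolled, at least 60% engage in at least 70% of the intervention modules".
- Section 11.1 (Aim 1 analysis): "of those enrolled, at least 60% engage with at least 70% of the intervention modules (modules engagement will be captured by the app".

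The design facts that bear on it are these:

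- Size: "We will conduct a single-site pilot randomized trial in 60 HCT survivors" (section 9.1).
- Allocation: "Patients will be randomized in 1:1 fashion" (section 9.1).
- Order of events: under section 9.2, patients enrol, complete the baseline measures, and are then randomised.
- Control arm: "Patients assigned to the enhanced standard care group will not receive the mobile app" (section 9.2).
- Source of the data: "Modules engagement will be captured by the app" (section 8.1).

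No section restricts the engagement denominator to the app arm. Section 9.3.2 does make that restriction for the System Usability Scale.

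**The concern.** The numerator can contain only patients who have the app. The denominator, as written, contains both arms. Half of it therefore counts as non-engaged by design, and the criterion measures the allocation ratio as much as it measures use of the app.

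What is at stake is the go/no-go decision on the primary endpoint. Applied literally, the rule declares the app not feasible whatever the patients do. Applied in any other way, it relies on a denominator that the plan does not state, so the primary rule is not fully pre-specified.

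**Working it through.** **Inputs**

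- Enrolled: N = 60 (sections 4.0 and 9.1).
- Allocation 1:1 (section 9.1), so about 30 per arm. Section 11.2 also works with 30 per group.
- Threshold: 60% (sections 1.2, 8.1 and 11.1).
- App access: intervention arm only (sections 9.1 and 9.2).

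**The plan's own figure.** The only precision stated is a 95% CI of +/- 12%, attached to the enrolment half. The Wald half-width is 1.96 × √(p(1 − p)/n). With p = 0.60 and n = 60 it is 1.96 × √(0.24/60) = 0.124, or 12.4 points, which agrees with the stated 12 after rounding.

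**The rule as written**

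1. Engaged patients needed: 0.60 × 60 = 36.
2. Patients who can engage: 60 × 1/2 = 30.
3. Highest attainable value: 30/60 = 50%, which is below 60%.
4. If 60% of the app arm engage, 0.60 × 30 = 18 patients, and the rule as written gives 18/60 = 30%.
5. Chance imbalance does not rescue it. At least 36 of the 60 would have to be allocated to the app, and at least 36 of those would have to engage. Even 35 app patients, all engaged, give 35/60 = 58.3%.

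**The rule with the app arm as denominator (n = 30)**

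1. Bar: 0.60 × 30 = 18 engaged patients.
2. Wald half-width at 60%: 1.96 × √(0.24/30) = 0.175, or 17.5 points. The exact (Clopper-Pearson) 95% interval for 18/30 is 40.6% to 77.3%.
3. Chance of meeting this half of the rule: P(X ≥ 18), with X binomial (30, p). The documents give no expected engagement rate, so the values of p are assumptions:

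| Assumed true engagement | P(X ≥ 18 of 30) |
|---|---|
| 50% | 0.181 |
| 60% | 0.578 |
| 70% | 0.916 |
| 80% | 0.997 |

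These probabilities describe the corrected criterion, not the defect, and they leave out the enrolment half.

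**The case against.** The strongest reply is that context settles the denominator. The rule judges the app, engagement is recorded by the app, and section 9.2 describes module completion and app-collected fidelity data under the intervention arm. A sensible analyst would count app patients only, and could decide that from the design without seeing any engagement data. Section 9.2 also uses enrolment loosely: it places the app tutorial at enrolment, although only app patients get it, after randomisation. On this view the fault is loose wording, not a miscalculation.

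Much of this stands. The app arm is very probably what is meant, and nothing in the documents shows that the denominator would be changed after the data are in. Three points remain.

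- In the same sentence, enrolment is what eligible patients do when they join the study, which covers both arms. The loose use in section 9.2 does not redefine the term.
- Section 9.3.2 shows that the authors write the restriction when they intend it.
- Setting aside the literal reading does not leave a single alternative. Section 9.2 places the clinician visit before the tablet is handed over, and section 13.0 allows withdrawal. The denominator could be all randomised to the app, all given a tablet, all who opened the app, or all who stayed on study. The choice can reverse the result. As an invented example, suppose 17 patients engage and 2 of 30 never receive a tablet: 17/30 = 56.7% fails and 17/28 = 60.7% passes.

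**Conclusion.** The concern holds. As written, the engagement half of the primary endpoint cannot exceed about 50% against a bar of 60%, and a result of 18 engaged among 30 app patients would be reported as 30%. This rests only on 60 enrolled, 1:1 allocation, and no app access for controls, all of which the protocol states. It does not need exactly equal arms, because any split that leaves fewer than 36 patients in the app arm gives the same answer.

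The likely intention is clear, but a primary decision rule that gives the wrong answer when followed as written has to be corrected. The pass probabilities are illustrations under assumed engagement rates, and the conclusion does not depend on them.

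**What to change.** In sections 1.2, 8.1 and 11.1, make the denominator all patients randomised to the app arm, and state the bar as 60% of that number: 18 or more if 30 are randomised. Randomisation is stratified and no block size is given, so the arm may not be exactly 30. Keeping the percentage as the rule, with 18 of 30 as the planned case, covers this (for example, 0.60 × 31 = 18.6, so 19 of 31).

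Say in the same place that everyone randomised to the app stays in the denominator, including patients who never receive the tablet, never open the app or withdraw. They count as non-engaged unless they reached 70% of the modules. This is a separate choice of analysis set, but without it the denominator is still open.

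Do not carry the +/- 12% over to this half. With 30 patients the half-width at 60% is about 17.5 points.

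The cost is one phrase in three places and one added sentence. No extra data, patients or procedures are needed.
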